Death from Exsanguination/Hemorrhage: Those patients who succumb on the operating table, IR suite or ICU due to uncontrolled coagulopathy or hemorrhage in the first 4 hours from arrival will have their mortality classified as exsanguination/hemorrhage. This will be determined by the individual trauma surgeon at the time of the event.

Acute Hemolytic Transfusion Reaction: We will utilize and characterize acute hemolytic transfusion reactions as defined by the CDC/National Healthcare Safety Network (NHSN) Hemovigilance Surveillance definition (www.cdc.gov/nhsn).

Linking Investigations in Trauma and Emergency Services

Task Order 2: Shock, Whole blood and Assessment of TBI (SWAT)

Galveston Orientation and Amnesia Test (GOAT): For TBI subjects, we will obtain the GOAT score at the time of discharge and the calculated score per standard methods.⁴⁸ (Figure 4) GOAT is a 10-item questionnaire used to quickly assess post-traumatic amnesia following head injury. The GOAT is read orally to the patient and may be easily administered at the bedside. The total score accounts for orientation of person, place, and time, and recollection of events pre and post-injury. Cutoff scores are available to identify abnormal, borderline, and normal orientation and it will additionally determine if a subject is able to provide continuing participation consent if consented by proxy.

Extended Glasgow Outcome Scale (6 months-GOSE): For TBI subjects, the GOSE score will be obtained at 6 months +/- 1month by hone survey or direct patient contact, whichever is feasible. For those TBI subjects who were unable to consent at discharge, the GOAT will be administered to assess their ability to provide direct consent, prior to the administration of the GOSE. When the assessment is done by phone, the verbal consent of participants who have regained the ability to consent, will be obtained to allow the GOSE to be completed. The score is able to characterize 6 month functional status into 8 well defined categories as shown in (Figure 5).

Classification of Mortality: Classification of the underlying mechanisms responsible for mortality are essential to appropriately characterize regional variation and preventable morbidity and mortality. Classification of mortality outcomes will be assigned at the level of the enrolling institution by the respective Site Investigator. A predefined list of mortality classifications will be provided and adjudicated upon at the site level and will include 1) Hemorrhage/Exsanguination, 2) TBI/herniation, 3) Multisystem Organ Failure, 4) Sepsis, 5) ARDS, 6) Coagulopathy, 7) Cardiac Arrest with 1-6, 8) Pulmonary Embolism, 9) Withdrawal of Care as well as other pertinent causes of injury related death.

The Galveston Orientation and Amnesia Test (GOAT)

Question	Error score	Notes
What is your name?	/ 2	Must give both first name and surname.
When were you born?	/ 4	Must give day, month, and year.
Where do you live?	/ 4	Town is sufficient.
Where are you now?		
(a) City	/ 5	Must give actual town.
(b) Building	/ 5	Usually in hospital or rehab center. Actual name necessary.
When were you admitted to this hospital?	/ 5	Date.
How did you get here?	/ 5	Mode of transport.
What is the first event you can remember after the injury?	/ 5	Any plausible event is sufficient (record answer)
Can you give some detail?	/ 5	Must give relevant detail.
Can you describe the last event you can recall before the accident?	/ 5	Any plausible event is sufficient (record answer)
What time is it now?	/ 5	1 for each half-hour error, etc.
What day of the week is it?	/ 3	1 for each day error, etc.
What day of the month is it? (i.e. the date)	/ 5	1 for each day error, etc.
What is the month?	/ 15	5 for each month error, etc.
What is the year?	/ 30	10 for each year error.
Total Error:		
100 - total error		Can be a negative number.

Figure 4

76-100 = Normal
66-75 = Borderline
< 66 = Impaired

1	Death	D
2	Vegetative state	VS
3	Lower severe disability	SD -
4	Upper severe disability	SD +
5	Lower moderate disability	MD -
6	Upper moderate disability	MD +
7	Lower good recovery	GR -
8	Upper good recovery	GR +

Figure 5

Linking Investigations in Trauma and Emergency Services

Task Order 2: Shock, Whole blood and Assessment of TBI (SWAT)

Clinical Laboratory Endpoints: Measurements of hemostasis (TEG, PT/PTT, INR; 0 hour(+ up to 2 hours), 4 hour (+/-2 hours) and 24 hour (+/-12 hours)) for all patients and hemolysis labs (LDH, haptoglobin, bilirubin; 0 hour (+up to 2 hours), 4 hour (+/- 2 hours), and 24 hour (+/- 12hours)) for all patients will be obtained. Plasma samples for mechanistic outcomes will be drawn, stored, aliquoted and banked. The timing of all laboratory draws will follow local state and central IRB guidelines and local IRB guidelines at those sites who do not cede those guidelines to the central IRB at the University of Pittsburgh. The specific planned timing of draws are shown in (**TABLE 1**).

Screening/Outcome Data and Sample Collection: Patients will be screened for inclusion and exclusion criteria for the cohort study at the time of or soon after trauma center arrival and will undergo early blood sampling (Arrival + up to 2hrs). LITES Network sites selected for the prospective cohort study will have the capabilities to follow the patient to the OR, IR suite or ICU to obtain samples/labs and to record and monitor ongoing resuscitation, blood and blood component transfusion, mortality time points, time to hemostasis and death due to exsanguination for up to 4 hours from arrival or until hemostasis is obtained or patient death occurs. Due to the early requirement of initial blood samples for this cohort study, a waiver of consent for the initial patient screening and early blood draws (first 36hrs post-injury) will be obtained from the

central IRB. When available, blood samples will be drawn from an indwelling catheter (arterial or venous). If no indwelling catheter is available, then venipuncture will be performed following standard state and IRB requirements. Clinical laboratory samples will be sent at each LITES Network site following each sites laboratory guideline/requirements. Blood samples for storage will be drawn, centrifuged, separated, processed, and stored at -80°C for batched shipping. The schedule of proposed data and sampling can be found in (**TABLE 1**).

+TBI Subjects						
TABLE 1.	Prehospital	Arrival (+up to2 hours)	4 hours (+/-2 hours post admission	24 hours (+/-12 hours) post admission	At discharge	At 6 months (+/- 1 month)
Procedures/Measurements						
Whole blood administration		x	X			
Component therapy administration		x	X			
Resuscitation data (WB, component transfusion)	x	x	X	x	x	
Survival		x	X	x	x	x
Mechanistic Banked Samples		x	X	x		
Hemostasis (PT, INR, TEG)		x	X	x		
Hemolysis Labs (Lactate Dehydrogenase, haptoglobin, bilirubin)		x	X	x		
Mechanistic Biomarkers		x	X	x		
CBC		x	x	x		
Serial Vitals (GCS, Blood pressure, Heart rate)	x	x	X	x		
GOAT (Galvenston Orientation Amnesia Test) +					x	
Extended Glasgow Coma Scale+						x

Linking Investigations in Trauma and Emergency Services

Task Order 2: Shock, Whole blood and Assessment of TBI (SWAT)

Clinical Coordinating Center: Clinical Coordination specific for Task Order 002 will be performed by MACRO (Multidisciplinary Acute Care Research Organization) and its dedicated research team at the University of Pittsburgh, including all regulatory requirements, provider and coordinator training and monitoring.

Institutional Review Board: A central IRB will be utilized at the University of Pittsburgh for the regulatory needs of the prospective observational cohort. All current LITES Network sites have IRBs which have experience and engagement with central IRB procedures. A waiver of initial consent up to 36 hours for screening and early sampling will be obtained from the central IRB allowing early sampling prior to consent.

Data Coordinating Center (DCC): Data Coordination specific for Task Order 002 will be performed by the DCC and led by [name] at the Graduate School of Public Health at the University of Pittsburgh. The DCC will coordinate all data collection and entry, management, security and confidentiality, data archiving, quality control and electronic medical record biomedical informatics as needed, as well as plan, coordinate and assist with all statistical analyses.

Data Collection: Based upon the ability to appropriately execute AIMs I and II, the associated hypotheses generated and the primary and secondary outcomes proposed, the following data will be obtained on enrolled patients:

Demographic and Injury Data: Age, gender, race/ethnicity, socioeconomic status, mechanism of injury, ISS, AIS scores, serial vitals (blood pressure, heart rate, respiratory rate), presence of TBI, ICU days, ventilator day, length of hospital stay, patient medication and past medical history.

Prehospital Data: Time of injury, scene time, serial vital signs (GCS, blood pressure, heart rate, respiratory rate), transport characteristics, times and description of prehospital interventions (intubation, lines), medications, medic qualifications, crystalloid fluids, blood or blood component transfusion, adjuncts including tranexamic acid.

ED Data: Arrival time, serial vitals (GCS, blood pressure, heart rate, respiratory rate), procedures, meds, resuscitation requirements (crystalloid, blood or blood component), adjuncts including tranexamic acid, factor VII, PCC, fibrinogen, ED disposition.

OR Data: Procedures, operations, resuscitation requirements (crystalloid, blood or blood component), type of anesthesia, vasopressor requirement, adjuncts including tranexamic acid, factor VII, PCC, fibrinogen, disposition, serial vitals (blood pressure, heart rate), OR disposition, core temperature.

Resuscitation Data: Whole blood resuscitation, time of transfusion, WB characteristics (titer, blood type, matched/unmatched, leukocyte reduced, platelet sparing), component blood resuscitation, time of transfusion, transfusion ratios, adjuncts including tranexamic acid, factor VII, PCC, fibrinogen.

Linking Investigations in Trauma and Emergency Services

Task Order 2: Shock, Whole blood and Assessment of TBI (SWAT)

Outcome Data: 4 hour, 6 hour and 24 hour mortality, MOF score (7days), nosocomial infection, acute hemolytic transfusion reaction, cause of mortality, time to hemostasis, venous thromboembolism (VTE).

TBI Data: Serial GCS, TBI severity (AIS codes), TBI classification (subarachnoid, subdural, intracerebral hemorrhage, epidural, +/- shift, multifocal with specific classification) TBI progression, ICP data, operative intervention, paralysis, benzodiazepine coma, hypertonic resuscitation, GOAT and GOSE at discharge and 6 months respectively.

Eligible patients for the prospective cohort study will have de-identified data configured for compilation into the web based data entry platform with appropriate and all security measures in conjunction the DCC.

Mechanistic Banked Samples: Samples within the 0 hour (+ up to 2 hours), at 4 hours (+/- 2 hours) and 24 hours (+/- 12 hours) will collected and stored for analyses. We will perform batched sample analyses of enrolled patient subgroups +/- coagulopathy and +/- TBI across the receipt of WB vs. component therapy. We will measure markers of endothelial cell injury including Syndecan-1 and Hyaluronan, markers of neurological injury and neuron cell death including S100B protein and Neuron Specific Enolase (NSE), and end points of coagulopathy including Thrombin-antithrombin complex (TAT), activated Protein C (aPC), tissue Plasminogen Activator (tPA) and Plasminogen Activator Inhibitor (PAI-1).

Sample Tracking, Management and Storage: After sample obtainment, processing and storage, samples will initially be batched sent to the University of Pittsburgh biological sample repository where it will be tracked, managed and stored until the necessary translational or mechanistic measurement are performed. The CCC and DCC have a long track record of coordinating such processes.

Power Analysis: The prospective cohort study will utilize time to 4 hour mortality for its primary outcome to power the study. Based upon the 6 LITES Network sites admission history that will be utilized and their respective volume of hemorrhagic shock patients meeting inclusion and exclusion criteria and a 3.5 year enrollment time period, we plan to initiate sampling on 1,050 patients over the enrollment time period of the study. With an 85% consent rate which is an estimate based upon prior studies of similar nature, we will consent for participation 892 patients for the study. With an estimate baseline rate of 4 hour mortality of 11.1 % derived from the PROPPR study, there will be 90% power to detect a hazard ratio of 1.9.

Calculations are based on the primary aim of the study based on the following assumptions:

- Type I error rate of 0.05
- Two-sided alternative hypothesis

Linking Investigations in Trauma and Emergency Services

Task Order 2: Shock, Whole blood and Assessment of TBI (SWAT)

- 6 sites will be involved, three whole blood and three component sites
- Each site will enroll 175 participants in 3.5 years of enrollment, of which, 85% will be eligible for the study (149)
- The calculations are based on Cox proportional hazard model
- A 4 hour event rate in the control (non-whole blood) group of 0.111

The power calculations for these secondary aims are presented below. When reporting the results of the analyses, caution will need to be taken with respect to the interpretation of the findings since they are secondary in nature.

The secondary outcomes in Aim 1B include binary outcome, continuous outcomes, and time to event outcomes. For the binary outcomes, the odds ratio that can be detected is presented in Table 1. For the continuous outcome, the effect size that can be detected is 0.13. Finally, for the time to event outcomes, the hazard ratio that can be detected over a range of event rates in the control group is also presented in Table 1.

Event Rate	.1	.2	.3	.4	.5	.6
Odds Ratio	1.76	1.56	1.49	1.46	1.46	1.48
Hazard Rate	2.69	1.70	.37	.30	.27	.30

- For Aim 1C, a nonparametric analysis of variance will be used to compare the distribution of the GOS-E between the two groups. An effect size of 0.17 could be detected.
- For aim 2A, a nonparametric analysis of variance will be used to compare the distribution of the GOS-E between the two groups. An effect size of 0.28 could be detected.
- For aim 2B, a nonparametric correlation coefficient will be used to assess the association between GOS-E and the area under the systolic blood pressure curve. For each, a 95% confidence interval with a width of 0.19 can be estimated.
- For all secondary analyses, the type I error rate was set to 0.05, with a two-sided alternative hypothesis, and 90% power. For the Aim 1, the sample size will be 1,190. For Aim 2, the sample size will be limited to those with a traumatic brain injury. For the purposes of this study, this is expected to be 35% or a total of 417 participants.

Analyses

AIM#1: The analysis will begin by describing the baseline demographic and clinical characteristics of the overall population and then stratified by whole blood usage. The characteristics will be

Linking Investigations in Trauma and Emergency Services

Task Order 2: Shock, Whole blood and Assessment of TBI (SWAT)

compared among those who receive and who do not receive whole blood. For discrete variables, proportions will be generated and a chi-square test will be used to test for differences between the proportions. For continuous characteristics, means (medians) and standard deviations (interquartile ranges) will be calculated and t-tests (Wilcoxon) will be used to compare the means (distributions) among those who receive and do not receive whole blood.

Hypothesis#1A: For the primary outcome, the time to death will be generated for each participant. Kaplan-Meier curves will be generated for each treatment group and a log-rank test will be used to compare the distribution of the cumulative proportion. A hierarchical Cox-proportional hazards regression model will be used to control for the within-institution clustering. The hierarchical Cox-proportional hazards regression model will then be used to assess the independent impact of whole blood on time to death after controlling for the clustering effect and potential confounding effects of baseline characteristics. The model will include main effects for whole blood usage and a propensity score for receiving whole blood. The propensity score for the use of whole blood will be generated using a boosted logistic regression model. The dependent variable in the model will be the use of whole blood and the independent variables will be the baseline characteristics of the population. The Cox-proportional hazards model will be used to estimate the cumulative probability of death 4 hours.

Hypothesis#1B: The analytic approach for the secondary outcomes included in Hypothesis#1B will vary based on the type of outcome. For binary outcomes (e.g., 12 hour and 24 hour mortality, death from exsanguination, incidence of MOF, nosocomial infection), the same analytic approach that was carried out for Hypothesis 1a will be implemented.

For continuous outcomes (e.g., transfusion ratios, blood transfusion requirements) a two-sided t-test for correlated means will be used to compare the means between those receiving and not receiving whole blood. A hierarchical analysis of variance model will be used to control for the within-institution clustering. The model will be used to assess the independent impact of whole blood after controlling for the clustering effect and the potential confounding. The model will include main effects for whole blood usage and propensity for receiving whole blood.

Finally, for time to event analyses (e.g., time to hemostasis), a bivariate hierarchical Cox proportional hazards regression model will be generated to compare the time to event between those receiving and those not receiving whole blood. Again, the hierarchical model will be used to control for within-institution clustering. In a second step, to determine the independent effect of whole blood after controlling for potential confounding effects, the propensity score will be added to the model.

Hypothesis#1C: A two-sided z-test for correlated proportions will be used to compare the distribution of GOS-E proportions between those receiving and not receiving whole blood. This

Linking Investigations in Trauma and Emergency Services

Task Order 2: Shock, Whole blood and Assessment of TBI (SWAT)

test will be used to control for the within-institution clustering. A hierarchical polytomous logistics regression model will then be used to assess the independent impact of whole blood after controlling for the clustering effect and the potential confounding effects of baseline characteristics. The model will include main effects for whole blood usage and propensity for receiving whole blood.

AIM#2: The analyses for the second aim will be restricted to the subset of participants who will be characterized as having a traumatic brain injury.

Hypothesis#2A: The analysis will begin by comparing the baseline characteristics of those with a prehospital and acute phase resuscitation systolic blood pressure greater than or equal to 120 mmHg to those who do not. For discrete variables, proportions will be generated and a chi-squared test will be used to test for differences between the proportions. For continuous characteristics, means (medians) and standard deviations (interquartile ranges) will be calculated and t-test (Wilcoxon) test will be used to compare the means (distributions) among those who receive and do not receive whole blood.

A two-sided z-test for correlated proportions will be used to compare the distribution proportions of GOS-E at 6-months between those with a prehospital and acute phase resuscitation systolic blood pressure greater than or equal to 120 mmHg to those who do not. A hierarchical polytomous logistics regression model will be used to control for the within-institution clustering. The model will be used to assess the independent impact of whole blood after controlling for the clustering effect and the potential confounding effects of baseline characteristics. As was done in Aim#1A, the propensity for a prehospital and acute phase resuscitation systolic blood pressure greater than or equal to 120 mmHg will be generated using a boosted logistic regression model which will include all baseline characteristics, including site and whole blood usage. The same analytic approach will be used to measure outcomes at discharge except a hierarchical logistic regression model will be used.

Hypothesis#2B: The area under the curve of systolic blood pressure during the prehospital and acute phase resuscitation will be generated for each study participant. The analysis will begin by comparing the baseline characteristics with the area under the curve. For discrete variables, bivariate linear regression models will be generated (area under the curve as the dependent variable and the discrete baseline characteristic as the independent variable). For continuous characteristics, the correlation will be assessed.

Hierarchical models will be used to adjust for within-institution clustering. Hierarchical bivariate linear regression models will be used to assess the association of baseline characteristics associated with area under the curve. A stratified propensity analysis will be used to estimate the association of area under the curve with GOS-E at six months. A hierarchical linear regression

Linking Investigations in Trauma and Emergency Services

Task Order 2: Shock, Whole blood and Assessment of TBI (SWAT)

model will be generated using the area under the curve as the dependent variable and the baseline characteristics as independent variables to generate an estimated area under the curve (propensity score) for each subject. The population will then be separated into five strata of equal sample size, based on the propensity. Within each stratum, the association of the area under the curve with outcome will be assessed using a hierarchical polytomous logistic regression model (outcome: GOS-E at six months, independent variable: area under the curve).

To determine the association across strata and if the association differs across strata, a multinomial polytomous regression model with GOS-E at six months as the outcome, area under the curve, an indicator of stratum, and the two-way interaction as independent variables will be fit.

The same analytic approach will be used to measure outcomes at discharge except a hierarchical logistic regression model will be used.

Subgroup Analysis: The general approach to assess the homogeneity of a treatment effect across subgroup will be to include an interaction term between the treatment variable and the characteristics defining the subgroup in the regression model. A statistically significant interaction term would indicate that the null hypothesis of a homogenous effect would be rejected indicating a differential effect of the treatment across the subgroups. For example, when examining the homogeneity of the effect of whole blood on the primary outcome among those with and without a traumatic brain injury, the hierarchical logistic model will be modified to include a main effect for traumatic brain injury and the two-way interaction between whole blood use and traumatic brain injury.

[figure not shown]
Interim Analysis: There will be two aspects of the interim analysis. First, for efficacy, the Lan and Demets approach will be utilized to conduct the interim efficacy analysis. This approach is preferable over other approaches because it is flexible to the number of interim analyses conducted during the course of the study. The Lan and DeMets approach requires the use of a spending function to allocate the type I error to the interim analysis. The O'Brien and Fleming spending function which minimizes the type I error allocated to the interim analysis, saving the vast majority for the primary analyses will be used. For the proposed interim analysis, assuming that 50% of the study will be completed, it is estimated that the type I error allocated to the interim analysis will be 0.005, leaving 0.048 of the type I error for the primary outcome analysis.

Linking Investigations in Trauma and Emergency Services

Task Order 2: Shock, Whole blood and Assessment of TBI (SWAT)

Time Line: The study will occur over a 4 year period with a 6 month start up period, an interim analysis at 2 years and a 3.5 year enrollment period.

Linking Investigations in Trauma and Emergency Services

Task Order 2: Shock, Whole blood and Assessment of TBI (SWAT)

BIBLIOGRAPHY

3. Hoyt DB. A clinical review of bleeding dilemmas in trauma. *Semin Hematol*. 2004;41(1 Suppl 1):40-43.

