Hypothesis #1B: *Whole blood resuscitation will be associated with a lower incidence of 12 hour and 24 hour mortality, a lower incidence of death from exsanguination, incidence of MOF, nosocomial infection, improved transfusion ratios, lower overall blood transfusion requirements and shorter time to hemostasis as compared to those resuscitated with component therapy.*

Hypothesis #1C: *Whole blood resuscitation will be associated with an improved Glasgow Outcome Score-Extended at 6 months post injury as compared to those resuscitated with component therapy in patients with traumatic brain injury.*

Hypothesis #2A: *A nadir prehospital and acute phase resuscitation systolic blood pressure greater than or equal to 120 mmHg will be associated with improved traumatic brain injury outcomes at discharge and at 6 months.*

Linking Investigations in Trauma and Emergency Services

Task Order 2: Shock, Whole blood and Assessment of TBI (SWAT)

Hypothesis #2B: *The magnitude of the dose depth curve of systolic blood pressure during the prehospital and acute phase resuscitation will be associated with neurological outcome differences at discharge and at 6 months following traumatic brain injury.*

Research Design and Methods

Study Design: The LITES Network will perform a multicenter, prospective, observational cohort study over a 4 year period to determine the impact of whole blood resuscitation in trauma patients with hemorrhagic shock at risk of large volume resuscitation with and without TBI. Early whole blood resuscitation will be compared to standard component resuscitation. The study will also further characterize blood pressure and resuscitation endpoints in poly-trauma patients with traumatic brain injury. Six trauma sites with appropriate characteristics will be selected from network sites across the country. (Figure 2)

Figure 2

Study Setting: The study will be performed utilizing busy level I trauma centers from within the LITES Network located across the country, at sites where either whole blood has currently been incorporated into standard of care or where component blood transfusion is being utilized for patients in hemorrhagic shock at risk for large volume resuscitation. Due to the paucity of trauma centers who are currently utilizing whole blood for trauma patients as standard of care, the potential to incorporate additional sites may be required over time.

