Component Transfusion Sites: Busy, Level 1 trauma centers from within the LITES Network will be selected based upon the ability to enroll patients with the proposed inclusion and exclusion criteria who currently utilize initial ratio based resuscitation (1:1:1 or 1:1:2) for patients at risk of large volume transfusion and are able to perform all necessary requirements for the planned prospective cohort study proposed. There is the potential for sites to differ based upon their current massive transfusion protocol and these standard practices will be documented for each site.

Primary TBI Subgroup Stratification: Presence or absence of Traumatic Brain Injury (TBI) will be the principle subgroup stratification for the study. Presence of TBI will be based upon CT imaging results (classification: subarachnoid, subdural, intracerebral hemorrhage, intracranial injury, epidural, +/- shift, multifocal with specific classification) and TBI severity will be characterized and grouped by GCS, Abbreviated Injury Severity (AIS) coding, ICD-10 head region severity scores

Linking Investigations in Trauma and Emergency Services

Task Order 2: Shock, Whole blood and Assessment of TBI (SWAT)

and Rotterdam CT scores. The data coordinating center will collect de-identified serial head CT images (first two performed) from all participating sites in patients with a head abbreviated injury score of 2 or greater (head AIS >2). These images will allow the determination of Rotterdam CT head scores to appropriately classify traumatic brain injury severity. Serial head CTs (first two) will also be assessed for progression of injury. An independent and blinded neuroradiologist from the University of Pittsburgh will provide the classification of brain injury.

Due to the nature of the population being studied, there will be patients who have clinically evident TBI but who do not have a head CT completed due to clinical intervention being a higher priority than diagnostic imaging. Often when patients require urgent clinical interventions, diagnostic scans (including CTs) are deferred until the patient is stabilized and the emergent issue is resolved. Unfortunately, this means that sometimes a patient expires during intervention, and a CT is never obtained. Therefore, patients who present in extremis with a clinically obvious TBI (eg: unhelmeted motorcyclist, falls from height, etc.) will be included in the TBI sub-group even if they do not have head CTs completed.

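### Hypothesis 2A classifies patients by nadir SBP over a window that can contain their death, so the 6-month GOS-E comparison leans towards SBP ≥120 to the extent that it does

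*Combined protocol and SAP*

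**What the plan says.** The hypothesis (Objectives/Specific Aims/Hypothesis, #2A) reads "A nadir prehospital and acute phase resuscitation systolic blood pressure greater than or equal to 120 mmHg will be associated with improved" outcomes of TBI, at discharge and at 6 months. The exposure is thus a minimum taken over a period that runs past arrival, not a baseline value.

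The analysis text (Analyses, AIM#2, Hypothesis#2A) uses the same phase and the same 120 mmHg cut-off without the word *nadir*. The 6-month step is described thus: "compare the distribution proportions of GOS-E at 6-months between those with a prehospital and acute phase resuscitation systolic blood pressure greater than or equal". All remaining TBI patients form the other group. The text does not say which reading classifies a patient.

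The outcome is GOS-E, said to "characterize 6 month functional status into 8 well defined categories"; Figure 5 gives category 1 to death. Aim 2 is "restricted to the subset of participants who will be characterized as having a traumatic brain injury", with no condition on survival.

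On early deaths, the Exclusion Criteria remove ED deaths only. Specific Outcome Definitions expects further early deaths after the ED: "Those patients who succumb on the operating table, IR suite or ICU due to uncontrolled coagulopathy or hemorrhage in the first 4 hours from arrival" are classified as hemorrhage deaths. Primary TBI Subgroup Stratification adds a rule for "patients who present in extremis with a clinically obvious TBI". Lack of imaging does not remove them from Aim 2, because they "will be included in the TBI sub-group even if they do not have head CTs completed".

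The planned adjustment is a hierarchical model for site, plus a boosted propensity score for SBP ≥120 built from baseline characteristics, site and whole blood use. The plan gives no end time for the acute phase, no landmark and no rule for arrest or terminal readings.

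**The concern.** If a patient dies of hemorrhage while pressure is still being recorded for the exposure, the falling pressure that precedes death puts that patient in the <120 group, and the death itself gives the worst GOS-E score. One event sets both variables. The ≥120 group then holds almost only people who lived through the window, while the <120 group holds the window survivors with a lower nadir plus nearly all window deaths.

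The hypothesis is directional and this mechanism pushes the same way. The propensity score works on characteristics fixed before the window. It cannot remove a link that is created afterwards by dying. The stated purpose of the aims includes insight into a resuscitation target in TBI with hemorrhagic shock, so a positive 2A result that is partly built in could be over-read.

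**Working it through.** **Inputs from the documents.** Control-group 4-hour mortality is 11.1% (Power Analysis). TBI share is 35%. The secondary power text uses 1,190 participants: 0.35 × 1,190 = 416.5, which reproduces its 417. The same section expects 892 consented participants: 0.35 × 892 = 312. Both sizes are shown.

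**The plan's own figure.** The plan gives 0.28 as the detectable effect for 2A at 90% power. With two equal groups of 417 in total, (1.960 + 1.282)/√(417 × 0.25) = 0.317. At 80% power with Wilcoxon efficiency 0.955, (1.960 + 0.842)/√(417 × 0.25 × 0.955) = 0.281. So 0.28 is not reproduced at 90%. That is a separate matter; 0.28 serves below only as a yardstick.

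**Assumptions not in the documents.**
- *m*, the share of TBI patients dying inside the window: 3%, 5% or 11.1%. The last borrows the control-group rate and places all those deaths in the window.
- *q*, the share of window survivors with nadir ≥120: 5% to 30%.
- *L*, later mortality, equal in both groups: 15% or 25%.
- Pressure has no effect, and every window death is classed <120.

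**Formulas.** The share of window deaths in the <120 group is s = m / [m + (1 − m)(1 − q)]; in the ≥120 group it is 0. Six-month death is L at ≥120 and s + L(1 − s) at <120, so the built-in gap is s(1 − L).

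**Worked case** (N = 312, m = 11.1%, q = 30%, L = 15%):
- 34.6 window deaths and 277.4 survivors; 83.2 patients at ≥120 and 228.8 at <120.
- s = 34.6/228.8 = 15.1%; gap = 0.151 × 0.85 = 12.9 points (27.9% v 15%).
- Pooled death rate 24.4%; standard error 0.0550 under equality, 0.0491 unpooled.
- Rejection ≈ Φ[(0.1287 − 1.96 × 0.0550)/0.0491] = Φ(0.42) ≈ 66%.

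**Range over q and L** (pooled two-proportion z-test on death, two-sided 5%):

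| m | s | gap, points | rejection, N = 312 | rejection, N = 417 |
|---|---|---|---|---|
| 3% | 3.2–4.2% | 2.4–3.6 | 5–11% | 5–13% |
| 5% | 5.2–7.0% | 3.9–5.9 | 5–21% | 6–27% |
| 11.1% | 11.6–15.1% | 8.7–12.9 | 8–66% | 10–80% |

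At q = 5% and m = 3% only about 15 patients are exposed (0.05 × 0.97 × 312). The approximation is rough there, and the low end means no visible inflation.

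**Check on the GOS-E scale.** A simulation with no effect of pressure used N = 417, a two-sided Wilcoxon test and 2,000 runs per setting. With 20% later mortality and m = 11.1%, a significant result favouring ≥120 occurred in 16%, 30% and 50% of runs at q = 10%, 20% and 30%, against a nominal 2.5% in that direction. The spurious standardized differences were 0.17, 0.19 and 0.22. At m = 3% the rates were about 4%, 6% and 8%. Restricting to patients alive at the end of the window brought two-sided rejection to 3.6–6.0% in every setting tried.

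**The case against.** Several objections have force.

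- **The exposure is not settled.** The analysis text compares patients "with a prehospital and acute phase resuscitation systolic blood pressure greater than or equal to 120 mmHg to those who do not" and omits *nadir*. Under an arrival or mean reading, death would not fix the exposure in this way. This stands as a condition on the point. It does not remove it, because the hypothesis itself specifies the nadir.
- **The window is not settled.** If the acute phase ended on leaving the ED, the ED-death exclusion would leave essentially no deaths inside it and the mechanism would nearly vanish. This also stands. Resuscitation is recorded for up to 4 hours, but that period is not tied to 2A.
- **Charted pressure is not physiological pressure.** A reader might infer that every early death necessarily falls below 120. The documents do not support that: recorded vitals may miss terminal values, and no rule says that arrest readings count. Nor are all unscanned early deaths kept in the TBI set; the text covers only those in extremis with clinically obvious TBI.
- **Not all of the gap need come from dying.** Many of these patients would already be below 120, since SBP ≤90 is one of the four qualifying signs. Where dying patients were lower beforehand, part of the gap is confounding by shock severity, which the propensity score may partly address. Yet few reclassifications are needed. Take N = 312, m = 11.1% and q = 10%, with pressure unrelated to death. Of 31.2 patients at ≥120, 3.5 would die in the window, the same 11.1% as elsewhere. Moving those 3.5 gives 0 of 27.7 against 34.6 of 284.3 (12.2%).
- **The tests above are unadjusted.** The planned final model is a propensity-adjusted hierarchical polytomous regression, and its rejection rate is not known. The plan also urges caution with secondary findings; that does not correct a bias with a known direction.

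**Conclusion.** The point holds conditionally. As Hypothesis 2A is worded, the 6-month GOS-E comparison is biased towards its own hypothesis to the extent that the exposure window contains deaths and terminal readings are counted. The baseline propensity score does not cure this.

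The direction follows from the definitions; the size is an assumption. If few deaths fall inside the window, the gap is a few points and the error rate close to nominal. If the full 11.1% do, the gap is about 9 to 13 points. The highest rejection rates need both 11.1% window mortality and 30% of survivors at ≥120. Few exposed patients lower the chance of a significant result but leave the direction unchanged.

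A reader might infer that 2A is bound to show a benefit, or that all of 2A is affected. Neither follows. The discharge GOAT can be obtained only in survivors, and the plan does not say how death counts in the discharge model, so the point is limited to 6-month GOS-E. It concerns a secondary hypothesis and should be settled before analysis.

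**What to change.** 1. Reconcile the hypothesis and the analysis text on one exposure definition: nadir SBP over a fixed window with a stated start and a stated end (the landmark), including how arrest or terminal readings are treated.
2. Make the main 2A comparison 6-month GOS-E among TBI patients alive at the landmark, keeping the planned site and propensity adjustment.
3. Report deaths inside the window separately, grouped by a reading fixed in advance, such as first recorded or arrival SBP.

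Serial vitals and survival are already in the data schedule, so the cost is analysis wording. The downside is that window deaths leave the main comparison, which becomes conditional on surviving the window and does not cover later pressures. A later landmark covers more of the pressure record but removes more deaths, so the time should be chosen without sight of outcomes by exposure. The landmark does not remove confounding by shock severity; that still rests on the propensity model.
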